9.3 Treatments

Study treatment

The analysis of study treatment data will be based on the safety set. The number of active and placebo injections received will be presented by treatment group.

The duration of exposure to study treatment will also be summarized by treatment group. In addition, the number and percentage of subjects with cumulative exposure levels (e.g. any exposure, ≥ 1 week, ≥ 2 weeks, ≥ 3 weeks, ≥ 4 weeks, ≥ 8 weeks, etc.) will be presented.

Prior and concomitant medication

Prior and concomitant medications will be summarized in separate tables by treatment group. Prior medications are defined as treatments taken and stopped prior to first dose of study treatment. Any medication given at least once between the day of first dose of randomized study treatment and the date of the last study visit will be a concomitant medication, including those which were started pre- BSL and continued into the period where study treatment is administered.

Medications will be presented in alphabetical order, by Anatomical Therapeutic Classification (ATC) codes and grouped by anatomical main group. Tables will show the overall number and percentage of subjects receiving at least one treatment of a particular ATC code and at least one treatment in a particular anatomical main group.

Significant prior and concomitant non-drug therapies and procedures will be summarized by primary system organ class and MedDRA preferred term.

The number and percentage of subjects receiving prior and concomitant PsA therapy will be presented by randomized treatment group as well as the reasons for stopping their therapies (primary lack of efficacy, secondary lack of efficacy, lack of tolerability, other).

9.4 Analysis of the primary variable(s)

Details of the testing strategy including primary and secondary endpoints are provided in [Section 9.5.1](#)

9.4.1 Variable(s)

The primary efficacy variable will be ACR20 response at Week 16. The analysis of the primary efficacy variable will be based on the FAS subjects. Primarily, CRP will be used instead of ESR to calculate ACR response; ESR will only be used in the event CRP is missing.

9.4.2 Statistical model, hypothesis, and method of analysis

The statistical hypothesis for ACR20 being tested is that there is no difference in the proportion of subjects fulfilling the ACR20 criteria at Week 16 in any of the secukinumab regimens vs. placebo regimen.

Let p_j denote the proportion of ACR20 responders at Week 16 for treatment regimens j , $j=0, 1, 2, 3$ where

- 0 corresponds to placebo regimen,
- 1 corresponds to secukinumab 150 mg PFS without loading,
- 2 corresponds to secukinumab 150 mg PFS with loading,
- 3 corresponds to secukinumab 300 mg PFS with loading,

In statistical terms, $H_0: p_j = p_0$, $H_{A_j}: p_j \neq p_0$, for the j^{th} secukinumab regimen, i.e.

$H_1:$ secukinumab 150 mg s.c. without loading is not different to placebo regimen with respect to signs and symptoms (ACR20 response) at Week 16

$H_2:$ secukinumab 150 mg s.c. with loading is not different to placebo regimen with respect to signs and symptoms (ACR20 response) at Week 16

$H_3:$ secukinumab 300 mg s.c. with loading is not different to placebo regimen with respect to signs and symptoms (ACR20 response) at Week 16

The primary endpoint of ACR20 at Week 16 in the FAS will be evaluated using a logistic regression with treatment and randomization stratum (TNF α status –naïve or IR) as factors and weight as a covariate. Odds ratios will be computed for comparisons of secukinumab regimens vs. placebo regimen utilizing the logistic regression model fitted.

9.4.3 Handling of missing values/censoring/discontinuations

Missing data for ACR20 response and other binary efficacy variables (e.g. ACR50, ACR70, HAQ-DI[®] response, etc.) for data up to Week 24 will be handled as follows:

- Subjects who drop out of the trial for any reason will be considered non-responders from the time they drop out through Week 24.
- Subjects who do not have the required data to compute ACR response (i.e. tender and swollen joint counts and at least three of the five ACR core set variables) at BSL and at the specific time point will be classified as non-responders.

Continuous variables (e.g. ACR components, DAS, etc.) will be analyzed using a mixed-effects repeated measures model (MMRM) which is valid under the missing at random (MAR) assumption. For analyses of these parameters, if all post-BSL values are missing then these missing values will not be imputed and this subject will be removed from the analysis of the

[figure not shown]
corresponding variable, i.e. it might be that the number of subjects providing data to an analysis is smaller than the number of subjects in the FAS.

Data collected after Week 24 will generally be presented as 'observed case'; i.e. all available data for each time point will be included in the analyses.

In general, the handling of data for subjects who are rescued at Week 16 will be handled in the following fashion for comparisons with placebo at Week 20 and Week 24:

- For each binary endpoint, a subject will be considered as a non-responder at Week 20/24 for that endpoint if the subject is a non-responder (including missing imputed non-responder) at Week 16. If a subject is a responder at Week 16, the actual value at Week 20/24 will be used (missing is considered as non-responder). This will be done for all treatment regimens in order to minimize bias.
- For continuous endpoints, the goal of the analyses would be to estimate what would have happened if the subjects had stayed on the original treatment. Thus, the data collected after the subject switches to secukinumab will be treated as missing for placebo subjects and will be analyzed using a MMRM which is valid under the missing at random (MAR) assumption. For secukinumab subjects, the actual values will be used in the analysis.

For comparisons between the active groups the rescue penalty will not be applied as the effect of rescuing is the same for both treatment groups (i.e. the subject continues to receive secukinumab 150 mg or 300 mg every 4 weeks).

9.5 Analysis of secondary variables

9.5.1 Efficacy variables

The secondary efficacy variables are listed below. Secondary efficacy variables will be analyzed using the FAS population unless otherwise specified.

- Change from baseline in van der Heijde modified total Sharp score at Week 24
- PASI75 response at Week 16
- PASI90 response at Week 16
- ACR50 response at Week 16
- Change from baseline in HAQ-DI[©] score at Week 16
- Change from baseline in DAS28-CRP at Week 16
- Presence of enthesitis at Week 16
- Presence of dactylitis at Week 16

Testing strategy

- The following hypotheses will be included in the testing strategy, and type-I-errors will be set such that a family-wise type-I-error of 5% is kept:

Primary objectives (detailed in [Section 9.4.2](#))

[figure not shown]
- H₁: secukinumab 300 mg is not different to placebo regimen with respect to ACR20 response at Week 16
- H₂: secukinumab 150 mg is not different to placebo regimen with respect to ACR20 response at Week 16
- H₃: secukinumab 150 mg No Load is not different to placebo regimen with respect to ACR20 response at Week 16

Secondary objectives:

- H₄: secukinumab 300 mg is not different to placebo regimen with respect to structural damage (van der Heijde modified total Sharp score) at Week 24
- H₅: secukinumab 150 mg is not different to placebo regimen with respect to structural damage (van der Heijde modified total Sharp score) at Week 24
- H₆: secukinumab 150 mg No Load is not different to placebo regimen with respect to structural damage (van der Heijde modified total Sharp score) at Week 24
- H₇: secukinumab 300 mg is not different to placebo regimen with respect to PASI75 response at Week 16 in the subset of subjects who have $\geq 3\%$ skin involvement with psoriasis
- H₈: secukinumab 150 mg is not different to placebo regimen with respect to PASI75 response at Week 16 in the subset of subjects who have $\geq 3\%$ skin involvement with psoriasis
- H₉: secukinumab 150 mg No Load is not different to placebo regimen with respect to PASI75 response at Week 16 in the subset of subjects who have $\geq 3\%$ skin involvement with psoriasis
- H₁₀: secukinumab 300 mg is not different to placebo regimen with respect to PASI90 response at Week 16 in the subset of subjects who have $\geq 3\%$ skin involvement with psoriasis

- H₁₁: secukinumab 150 mg is not different to placebo regimen with respect to PASI90 response at Week 16 in the subset of subjects who have $\geq 3\%$ skin involvement with psoriasis
- H₁₂: secukinumab 150 mg No Load is not different to placebo regimen with respect to PASI90 response at Week 16 in the subset of subjects who have $\geq 3\%$ skin involvement with psoriasis
- H₁₃: secukinumab 300 mg is not different to placebo regimen with respect to ACR50 response at Week 16
- H₁₄: secukinumab 150 mg is not different to placebo regimen with respect to ACR50 response at Week 16
- H₁₅: secukinumab 150 mg No Load is not different to placebo regimen with respect to ACR50 response at Week 16
- H₁₆: secukinumab 300 mg is not different to placebo regimen with respect to the change from baseline in HAQ-DI[®] at Week 16
- H₁₇: secukinumab 150 mg is not different to placebo regimen with respect to the change from baseline in HAQ-DI[®] at Week 16
- H₁₈: secukinumab 150 mg No Load is not different to placebo regimen with respect to the change from baseline in HAQ-DI[®] at Week 16
- H₁₉: secukinumab 300 mg is not different to placebo regimen with respect to the change from baseline in DAS28-CRP at Week 16
- H₂₀: secukinumab 150 mg is not different to placebo regimen with respect to the change from baseline in DAS28-CRP at Week 16
- H₂₁: secukinumab 150 mg No Load is not different to placebo regimen with respect to the change from baseline in DAS28-CRP at Week 16
- H₂₂: secukinumab 300 mg is not different to placebo regimen with respect to presence of enthesitis at Week 16 in the subset of subjects who have enthesitis at BSL
- H₂₃: secukinumab 150 mg is not different to placebo regimen with respect to presence of enthesitis at Week 16 in the subset of subjects who have enthesitis at BSL
- H₂₄: secukinumab 150 mg No Load is not different to placebo regimen with respect to presence of enthesitis at Week 16 in the subset of subjects who have enthesitis at BSL
- H₂₅: secukinumab 300 mg is not different to placebo regimen with respect to presence of dactylitis at Week 16 in the subset of subjects who have dactylitis at BSL
- H₂₆: secukinumab 150 mg is not different to placebo regimen with respect to presence of dactylitis at Week 16 in the subset of subjects who have dactylitis at BSL
- H₂₇: secukinumab 150 mg No Load is not different to placebo regimen with respect to presence of dactylitis at Week 16 in the subset of subjects who have dactylitis at BSL

The graphical approach of ([Bretz et al 2009](#)) for sequentially rejective testing procedures is used to illustrate the testing strategy:

Figure 9-1 Hierarchical testing strategy

The family-wise error will be set to $\alpha=5\%$ and it will be controlled with the proposed hierarchical testing strategy. With this approach, the hypotheses will be separated into two families. The first family will include hypotheses of ACR20 at Week 16 and mTSS at Week 24 (H₁ through H₆). The Hypotheses of additional signs and symptoms (H₇ to H₂₄) will be the second family. The second family hypotheses will be tested only when all hypotheses in the first family have been rejected.

Each of the hypotheses (H₁, H₂ and H₃) for the primary objective (ACR20 at Week 16) for each secukinumab regimen vs. placebo will be tested simultaneously at $\alpha/3$. Then based on the rejection of one or more (of H₁, H₂ and H₃), the mTSS at Week 24 endpoint will be tested hierarchically for each dose (through H₄, H₅ or H₆) at the level of $\alpha/3$. If anyone is rejected, then half (1/2) of $\alpha/3$ will be passed on to each of the other two hypotheses of ACR20 if they were not already rejected.

If H_1 to H_6 in the first family are all rejected, then AIN457 300 mg for all variables in the second family will be tested hierarchically at α starting from PASI75 (H_7). If all variables in AIN457 300 mg group are rejected then test AIN457 150 mg group and finally AIN 457 150 mg No Load group for all variables in hierarchy. Of note, in the description above, rejection of a hypothesis refers to rejection of the two-sided hypothesis; however the level of a rejected hypothesis is only passed on according to the graphical procedure for the test of another hypothesis if the treatment effect is in favor of secukinumab.

ACR50 at Week 16

Response at Week 16 to ACR50 in the FAS will be evaluated using a logistic regression model with treatment and randomization stratum (TNF α status – naïve or IR) as factors and weight as a covariate.

Joint/bone structural damage at Week 24

The change at Week 24 from BSL van der Heijde total modified Sharp score will be evaluated using a non-parametric ANCOVA model with treatment regimen and randomization stratum (TNF α status – naïve or IR) as factors, and weight and BSL van der Heijde total modified Sharp score as covariates. For subjects either on placebo or active, who have a missing Sharp score at Week 24, linear extrapolation will be used to impute the value at Week 24 if at least two assessments exist before Week 24 (including baseline assessment).

For placebo subjects who meet the criteria for early escape at Week 16, they will be treated as missing for placebo treatment and linear extrapolation will be used to impute the value at Week 24. If BSL or all post- BSL total modified Sharp score/s is/are missing for a subject, the subject will be excluded from the analyses.

Sensitivity analysis will be performed with possibly valid missing data imputation methods including:

- Using all available Week 24 data for early escape for all subjects (placebo and active);
- LOCF instead of linear extrapolation;
- Multiple imputation and tipping point;
- Binary endpoint analysis (no disease progression defined as those subjects who have a change in mTSS at Week 24 relative to baseline ≤ 0.5) with logistic model:
 - LOCF;
 - Multiple imputation;
 - Tipping point.

Physical function (HAQ-DI $^{\circ}$)

Between-treatment differences in the change in HAQ-DI $^{\circ}$ will be evaluated using a MMRM with treatment regimen, analysis visit and TNF-alpha inhibitor status as factors, and weight and BSL HAQ-DI $^{\circ}$ score as continuous covariates. Treatment by analysis visit and BSL by analysis visit will be included as interaction terms in the model. An unstructured covariance structure will be assumed for this model. The significance of the treatment effects for secukinumab

regimens at different analysis visits will be determined from the pairwise comparisons performed between secukinumab regimens and placebo at the appropriate analysis visits.

Dactylitis at Week 16

Presence of dactylitis at Week 16 in the subset of subjects who have dactylitis at BSL will be evaluated using a logistic regression model with treatment and randomization stratum (TNF α status –naïve or IR) as factors and weight as a covariate.

Enthesitis at Week 16

[figure not shown]
Presence of enthesitis at Week 16 in the subset of subjects who have enthesitis at BSL will be evaluated using a logistic regression model with treatment and randomization stratum (TNF α status –naïve or IR) as factors and weight as a covariate.

PASI75 and PASI90 response

PASI75 response and PASI90 at Week 16 will be evaluated for those subjects in whom the assessment occurred due to sufficient skin involvement (at least 3% BSA affected with psoriasis) (which is planned to be a subset of the FAS). These binary variables will be evaluated in the same fashion as ACR response, i.e. a logistic regression model with treatment and randomization strata as factors and weight as a covariate.

Changes in DAS28-CRP

Between-treatment differences in the change from baseline in DAS28-CRP will be compared by means of a MMRM with treatment regimen, analysis visit, and TNF-alpha inhibitor status as factors, and weight and BSL as continuous covariates. Treatment by analysis visit and BSL by analysis visit will be included as interaction terms in the model. An unstructured covariance structure will be assumed for this model. The significance of the treatment effects for secukinumab regimens at different analysis visits will be determined from the pairwise comparisons performed between secukinumab regimens and placebo at the appropriate analysis visits.

9.5.3 Safety variables

Adverse events

Treatment emergent AEs (events that started after the first dose of study treatment or events present prior to the first dose of study treatment but increased in severity based on preferred term) will be summarized up to 12 weeks (84 days) after the last dose.

AEs will be summarized by presenting, for each treatment group, the number and percentage of subjects having any AE, having an AE in each primary system organ class and having each individual AE (preferred term). Summaries will also be presented for AEs by severity and for study treatment related AEs. If a subject reported more than one AE with the same preferred term, the AE with the greatest severity will be presented. If a subject reported more than one AE within the same primary system organ class, the subject will be counted only once with the greatest severity at the system organ class level, where applicable. SAEs will also be summarized.

These summaries may be presented separately by study periods.

As appropriate, the incidence of AEs will be presented per 100 subject years of exposure.

Separate summaries will be provided for death, SAE, other significant AEs leading to discontinuation and AEs leading to dose adjustment (including study treatment discontinuation).

A graphical display of relative frequencies within system organ classes and relative risks, as appropriate, will be presented.

[figure not shown]
When adjudication is required of major cardiovascular events, a summary of those types of events as reported by the investigator and confirmed by adjudication will be provided.

Laboratory data

The summary of laboratory evaluations will be presented for three groups of laboratory tests (hematology, serum chemistry and urinalysis). Descriptive summary statistics for the change from baseline to each study visit will be presented. These descriptive summaries will be presented by test group, laboratory test and treatment group. Change from baseline will only be summarized for subjects with both BSL and post- BSL.

For each parameter, the maximum change from baseline within each study period will be evaluated analogously.

In addition, shift tables will be provided for all parameters to compare a subject's BSL laboratory evaluation relative to the visit's observed value. For the shift tables, the normal laboratory ranges will be used to evaluate whether a particular laboratory test value was normal, low, or high for each visit value relative to whether or not the BSL value was normal, low, or high. These summaries will be presented by laboratory test and treatment group. Shifts will be presented by visit as well as for most extreme values post- BSL.

Vital signs

Analysis of the vital sign measurements using summary statistics for the change from baseline for each post- BSL visit will be performed. These descriptive summaries will be presented by vital sign and treatment group. Change from baseline will only be summarized for subjects with both BSL and post- BSL values.

ECG

Summary statistics will be presented for ECG variables by visit and treatment group. Qualitative changes will be summarized.

9.5.4 Health-related Quality of Life

All Health-related Quality of Life will be evaluated based on FAS.

9.6 Interim analyses

The primary endpoint analysis will be performed in an interim analysis after all subjects have completed the Week 24 visit. The investigators, site personnel and monitors will continue to remain blinded to the original treatment assignment that each subject received at randomization until after the database lock for Week 52 analysis.

Subsequent to the primary endpoint analysis, additional analyses are planned after subjects have completed the Week 52 assessments and may be used for regulatory submission and/or publication purposes. The final analysis will be conducted after all subjects complete the study. Additional analyses may be performed to support interactions with health authorities, as necessary.

9.7 Sample size calculation

A 5% two-sided type I error rate will be used to control for type I error. Three secukinumab regimens will be tested versus placebo with respect to the primary endpoint (ACR20 response), thus the type-I-error will be split to 1.67% two-sided for each comparison. Sample sizes will be based on this type I error assumption. With an assumed placebo rate of 15% and secukinumab 51% (FUTURE 2), the study is over 99% powered to detect a treatment difference of ACR20 in the FAS population, assuming 220 subjects in a secukinumab treatment group, and 330 subjects in the placebo group (Fisher's exact test, nQuery 7.0). This power is applicable for all three dose regimens, as the sample size is driven by structural endpoint.

Power for secondary variables was calculated using a two-sided 1.67% type I error. With an assumed placebo rate of 7% and secukinumab 35% (FUTURE 2), the study is over 99% powered to detect a treatment difference of ACR50 in the full FAS population, assuming 220 subjects in a secukinumab treatment group, and 330 subjects in the placebo group (Fisher's exact test, nQuery 7.0).

For structural endpoint, historical data (FUTURE 1) showed a standard deviation of 1.132 on active treatment and 2.435 on placebo at Week 24, and a difference of 0.52. Using the above

assumptions, there is 83% power to show statistically significant differences assuming 220 subjects in a secukinumab group and 330 subjects in the placebo group (Satterthwaite t-test, nQuery 7.0).

A standard deviation of approximately 0.49 and a treatment difference of 0.17 has been observed for the change from baseline at Week 24 in HAQ-DI[®] (FUTURE 2). Using those assumptions, the study has approximately 94% power to detect a difference between secukinumab and placebo (Two group t-test, nQuery Advisor 7.0), assuming 220 subjects in a secukinumab treatment group and 330 subjects in the placebo group.

For the presence of dactylitis in the subset of subject who have dactylitis at BSL, with an assumed placebo rate of 85% and secukinumab 50% (FUTURE 2), there is about 99% power to show statistically significant difference between secukinumab (110) and placebo (165 subjects), assuming 50% subject have dactylitis at BSL (Fisher's exact test, nQuery 7.0).

For the presence of enthesitis in the subset of subject who have enthesitis at BSL, with an assumed placebo rate of 79% and secukinumab 58% (FUTURE 2), there is about 94% power to show statistically significant difference between secukinumab (132 subjects) and placebo (198 subjects), assuming 60% subjects have enthesitis at BSL (Fisher's exact test, nQuery 7.0).

With an assumed placebo rate of 16% and secukinumab 48% (FUTURE 2), the study is over 99% powered to detect a treatment difference of PASI75 in the FAS population, assuming 110 subjects in a secukinumab treatment group, and 165 subjects in the placebo group. It is assumed that about 50% of enrolled subjects have $\geq 3\%$ skin involvement.

A difference of 0.62 and standard deviation of 1.04 has been observed for the change from baseline in DAS28-CRP (FUTURE 2). With these assumptions, the study has over 99% power to detect a difference between secukinumab and placebo (Two group t-test, nQuery Advisor 7.0), assuming 220 subjects in a secukinumab treatment group, and 330 subjects in the placebo group.

With an assumed placebo rate of 9% and secukinumab 33% (FUTURE 2), the study is over 99% powered to detect a treatment difference of PASI90 in the FAS population, assuming 110 subjects in a secukinumab treatment group, and 165 subjects in the placebo group. It is assumed that about 50% of enrolled subjects have $\geq 3\%$ skin involvement.

10 Ethical considerations

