Each of the hypotheses (H1, H2 and H3) for the primary objective (ACR20 at Week 16) for each secukinumab regimen vs. placebo will be tested simultaneously at  $\alpha/3$ . Then based on the rejection of one or more (of H1, H2 and H3), the vdH-mTSS at Week 24 endpoint will be tested hierarchically for each dose (through H4, H5 or H6) at the level of  $\alpha/3$ . If anyone is rejected, then half (1/2) of  $\alpha/3$  will be passed on to each of the other two hypotheses of ACR20 if they were not already rejected.

If  $H_1$  to  $H_6$  in the first family are all rejected, then AIN457 300 mg for all variables in the second family will be tested hierarchically at  $\alpha$  starting from PASI75 ( $H_7$ ). If all variables in AIN457 300 mg group are rejected then test AIN457 150 mg group and finally AIN 457 150 mg No Load group for all variables in hierarchy. Of note, in the description above, rejection of a hypothesis refers to rejection of the two-sided hypothesis; however the level of a rejected hypothesis is only passed on according to the graphical procedure for the test of another hypothesis if the treatment effect is in favor of secukinumab.

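### The 94% to over 99% power stated for the second-family endpoints ignores the gate: on the plan's own mTSS figures, any second-family test is reached with probability at most 92%, and about 84% under the cited graphical procedure

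*Protocol*

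**What the plan says.** Protocol 9.7, repeated in SAP 3, introduces the secondary powers with "Power for secondary variables was calculated using a two-sided 1.67% type I error". Each compares one secukinumab group with placebo. The stated values are 94% for HAQ-DI, about 94% for enthesitis, and over 99% for ACR50, PASI75, PASI90 and DAS28-CRP. For mTSS the section says "there is 83% power to show statistically significant differences assuming 220 subjects in a secukinumab group and 330 subjects in the placebo group", and it notes that this endpoint drives the sample size.

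The testing strategy in Protocol 9.5.1 and SAP 2.6.2.1 puts ACR20 and mTSS for all three regimens (H1 to H6) in a first family. The other endpoints come behind a gate: "The second family hypotheses will be tested only when all hypotheses in the first family have been rejected". Once the gate is passed, "then AIN457 300 mg for all variables in the second family will be tested hierarchically at" the full alpha, starting from PASI75. The order of regimens follows: "If all variables in AIN457 300 mg group are rejected then test AIN457 150 mg group", and 150 mg No Load comes last.

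Within the first family, each mTSS hypothesis follows its own ACR20 hypothesis at alpha/3. When one is rejected, half of its level "will be passed on to each of the other two hypotheses of ACR20 if they were not already rejected". The method is described as a graphical approach that "for sequentially rejective testing procedures is used to illustrate the testing strategy". SAP 2.6.2.1 adds that "the level of a rejected hypothesis is only passed on according to the graphical procedure" when the effect favours secukinumab.

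**The concern.** The power section and the testing strategy describe two different procedures. No second-family hypothesis is tested at 1.67%, and none is tested without the gate. Three of the six gate tests are mTSS tests with only 83% power each, so the gate is much harder to pass than the second-family powers suggest. Neither power section calls its figures marginal or refers to the testing strategy.

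If a single regimen misses on mTSS, no second-family endpoint can be tested confirmatorily for any regimen. A stated power of 94% or more implies a failure risk of 6% or less. That leaves out the risk of never reaching the test.

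**Working it through.** **Inputs (Protocol 9.7).** mTSS difference 0.52; SD 1.132 on active and 2.435 on placebo; 220 and 330 subjects; Satterthwaite t-test; alpha 5% two-sided, alpha/3 = 1.67%. ACR20 at 15% against 51% has power above 99.9% at 1.67%, so mTSS alone decides the gate.

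**Step 1: reproduce the stated figures.**
- Variance terms: 1.132²/220 = 0.00582 and 2.435²/330 = 0.01797.
- SE = √(0.00582 + 0.01797) = 0.1542; Satterthwaite df = 498; non-centrality = 0.52/0.1542 = 3.371.
- mTSS power at alpha/3 is 83.3% (stated 83%).
- The second-family figures also reproduce as marginal powers:

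| Endpoint | Stated | At 1.67% | At 5% |
|---|---|---|---|
| PASI75 | over 99% | 99.95% | 99.99% |
| PASI90 | over 99% | 99.5% | 99.8% |
| ACR50 | over 99% | >99.9% | >99.9% |
| HAQ-DI | 94% | 94.3% | 97.8% |
| DAS28-CRP | over 99% | >99.9% | >99.9% |
| Enthesitis | about 94% | 94.8% | 98.0% |

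**Step 2: ceiling that needs no graph.** Under any recycling, rejecting all three mTSS hypotheses requires each p-value to be at most 5%. One mTSS test at 5% has power 92.0%. The gate probability cannot exceed this for any correlation, and it lies below the lowest stated second-family power.

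**Step 3: shared placebo.** The three mTSS tests are correlated through the placebo arm: 0.01797/(0.00582 + 0.01797) = 0.755. In a simulation of 4 million draws with difference 0.52 in all regimens, all three succeed at 5% in 85.2% of trials.

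**Step 4: level recycling.** The prose gives these edges: each ACR20 hypothesis to its own mTSS hypothesis with weight 1, and each mTSS hypothesis to the other two ACR20 hypotheses with weight 1/2 each. After H1 to H3 are rejected, the standard graph update leaves weights of 1/2 between mTSS hypotheses. The first mTSS rejection raises each remaining one to alpha/3 + alpha/6 = alpha/2. The weight between the last two becomes (1/2 + 1/4)/(1 − 1/4) = 1, so the final test is at alpha. The ordered p-values must therefore lie within alpha/3, alpha/2 and alpha. The simulated chance is about 84%. If mTSS stayed at alpha/3 throughout, it would be 72%.

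**Step 5: sensitivity of the 84%.**

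| mTSS difference | Gate probability |
|---|---|
| 0.45, all regimens | 69% |
| 0.48, all regimens | 76% |
| 0.52, all regimens | 84% |
| 0.56, all regimens | 90% |
| 0.60, all regimens | 94% |
| 0.60 / 0.52 / 0.45 | 79% |
| 0.52 / 0.52 / 0.45 | 78% |

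The common difference would have to be about 0.60 for the gate to reach 94%, and about 0.72 for 99%.

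**The case against.** Quoting marginal power is common practice, and no stated number is miscalculated. The section gives the level, the test and the group sizes, says that the structural endpoint drives the sample size, and prints the 83%. A careful reader could combine this with the gate. The 1.67% is also conservative, because second-family tests run at 5%, where HAQ-DI and enthesitis have about 98% marginal power. These points stand, but higher conditional power cannot lift the overall power above the gate probability, and the section does not send the reader to the gate.

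The 84% depends on a graph whose figure is not in the text reviewed, on a common difference of 0.52, and on a t-test. The planned analysis is a non-parametric ANCOVA, with linear extrapolation for placebo subjects who escape at Week 16 (Protocol 9.5.1). Protocol 1.1 says that the one earlier study with structural data had no 300 mg regimen and did not compare loading with no loading, so equal effects are indeed an assumption.

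The 92% ceiling does not depend on the graph, but it does depend on the inputs. At a difference of 0.56, one mTSS test at 5% has 95.2% power. At 0.52 with an illustrative 10% variance reduction from covariates it has 94.4%. Both exceed the lowest stated 94%. These are limits on precision. The t-test with 0.52 is the sponsor's own basis for 83%, and keeping mTSS at alpha/3 would make the result worse.

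**Conclusion.** The concern holds. The stated second-family powers are correct marginal figures, but the planned procedure does not deliver them. On the plan's own inputs, the risk that no second-family endpoint is tested is at least 8%, and about 16% under the cited graphical procedure.

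This rests on the t-test model, ACR20 power of practically 1, a difference of 0.52 in all three regimens, and, for the 84%, the standard graph update applied to the edges in the prose. The ceiling of 92% needs no assumption about the graph or the correlation, and it applies if even one regimen has a true difference of 0.52 or less.

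**What to change.** In SAP 3, and in Protocol 9.7 at the next amendment:

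1. Label the secondary powers as marginal, per comparison, at two-sided 1.67%.
2. Refer to the testing strategy.
3. Add text such as:

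> Under the testing strategy all of H1 to H6 are rejected with probability about 84% (t-test model, mTSS difference 0.52 in all regimens; about 69% to 94% for common differences of 0.45 to 0.60). This is the upper limit on the power of each second-family test, which is made at two-sided 5%.

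The sponsor should confirm the figure against its own graph before inserting it. About 72% applies only if that graph passes no level between mTSS hypotheses. The unequal-effect cases (78% to 79%) could be added.

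The cost is a less favourable stated power. Protocol 11.1 requires a written amendment for any change to 9.7, so that edit can wait for the next one while the SAP carries the text. Tests, error control and sample size stay as they are.
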